eicosapentaenoic acid (EPA) and docosahexaenoic acid (DHA) ethyl esters. Lovaza® is provided by GlaxoSmithKline, who has authorized the FDA center for Drug Evaluation and Research, Division of Metabolic and Endocrine Drug Products to reference Lovaza® Capsules IND # 45,998. Bottles are labeled to comply with study requirements and applicable regulations for investigational drug use. Bottles with study agent will be stored at controlled room temperature (15-30 °C). The products are both standardized and examined for content, stability and bioavailability and the study will be conducted with an investigator-initiated new drug (IND) approval from the Food and Drug Administration (FDA) as mandated by the National Cancer Institute for Phase I-III clinical trials. Use of n-3 fatty acids may decrease platelet aggregation and subjects with evidence of bleeding diathesis or coagulopathy will not be included in this study and those with concurrent use of Coumadin or warfarin will be observed closely. The follow-up monitoring for PT, PTT for patients on warfarin and/or Coumadin will follow the standard of care as dictated by the prescribing physician. The prescribing MD will be notified by the research staff of the subject participating in the study, and monitors for PT, PTT will be obtained from patients during the monthly clinic visits.

5.2 Rationale for Dose selection and Administration:

5.2.1 Study Agent Lovaza® There is no established Dietary Reference Intake for n-3 fatty acids, yet the Adequate Intake (AI) is set at 1.6 and 1.1 grams/day for men and women respectively. While intake in the United States occurs at much lower than the proposed AI and no signs of deficiency are observed, the AI is proposed to provide optimal health benefits associated with consuming n-3 fatty acids. There is no Upper Limit established for n-3 fatty acids. In early studies using fish oil capsules, we and others have demonstrated the safety of administering 2-6 gms of EPA per day. Anticachectic effects were seen with these doses, with no adverse effects, however, there was no greater response with 6 gms per day relative to 2-4 grams/day. Therefore, the dose selected for this pilot clinical trial, 4 grams per day is comparable to the safe but effective dosage used in our preliminary studies and that of others. Currently prescription doses of 4 grams a day of Lovaza® is used and approved by the FDA to treat hypertriglyceridemia. Furthermore, one, 3 to 4 oz serving of cold water fish such as salmon or sardines contains approximately 1.0-1.5 gms of n-3 fatty acids. The participant will be provided packages of the agent in a capsule form and instructed on compliance, intake, duration of intervention, and monitors to be completed by the research staff. Subjects will be instructed to consume 4 gm Lovaza® in a divided dose (2 gm in the morning and 2 gm at night, to provide a total of 4 gm/day) with meals for a period of 3 months.

5.2.2 Blueberry anthocyanins (VitaBlue): Similarly, there is no established Dietary Reference Intake of the constituents of anthocyanins. The average daily consumption of anthocyanins in a western diet is estimated to be 100 mg/day.¹²⁰ Anthocyanins are rapidly absorbed and metabolized extensively following a moderate-to-high oral dose in humans. Studies have indicated anywhere from 4-6 hours half-life with complete excretion of parent compound as well as metabolites within 24 hours both in urine and plasma, indicating the need for a dose every 6- 8 hours to have consistent exposure¹²¹. Similarly administration of anthocyanins at doses ranging from 0.5-2.0 grams daily for 7 days in colorectal cancer patients with dose dependant concentrations detected in plasma and urine with no toxicities.¹²⁰ Studies utilizing anthocyanins at doses of 1.4 grams/day (Mitroslect, Indena S.p.A.) administered as 0.47 grams/capsule TID are currently in progress to provide active cellular antioxidant protection, inhibit inflammatory gene expression and consequently protect against oxidant-induced and inflammatory cell damage and cytotoxicity in obesity-induced inflammation and insulin resistance (NCT01180712) in 40-60 year old males for 21 days. In summary, repeated administration of anthocyanins exerts pharmacodynamic effects and generates concentrations of anthocyanins in human plasma as well as urine with no toxicity. We will thus use a dose of 0.47 grams/capsule dose of anthocyanins TID to total 1.4 grams per day, similar to the dose used in these chemoprevention trials.

5.3 Availability: VitaBlue will be obtained from VDF FutureCeuticals'. The product has earned self-affirmed GRAS (generally recognized as safe) status for use in food and beverages after a comprehensive review by an independent panel of experts. Lovaza® is manufactured and distributed by Glaxo Smith-Kline laboratories and will be obtained from them for use in this study. The capsules have been manufactured by our team utilizing standards established by the FDA in a certified Compounding Center (Carrollwood Compounding Center and Pharmacy) and verified by the Center and by an independent testing group to assure consistent quality of the active agent contained in each capsule. The FDA has verified all these aspects of the agent as well as the placebo manufactured for this study and has provided us an IND approval of

these agents used in this study. [name] team currently holds 3 INDs for agents and placebos developed and approved by the FDA using the same methods for use in her research approved by this IRB.

Placebo's were also manufactured by Carrollwood Compounding Center and Pharmacy.

5.4 Agent Distribution: Agents will only be released by the Investigational pharmacy at MCC after documentation of IRB approval of the protocol and consent is provided and the collection of all essential documents is complete (*e.g.*, signed 1572, current CV, medical license, and lab certifications, *etc.*) and new documents have been submitted to the FDA for the IND.

5.5 Agent Accountability: The PI, or a responsible party designated by the investigator (Investigational pharmacy at MCC), will maintain a careful record of receipt, disposition, and return of all study drugs on the Investigational Agent Accountability Record. All study drug supplies will be kept in a locked, limited access area. The study drug will not be used outside the context of the protocol. Under no circumstances will the investigator or other site personnel supply study drug to other investigators, patients, or clinics, or allow supplies to be used other than directed by this protocol. Study agent will not be transferred from one participant to another.

The investigator will maintain records documenting the receipt, use, loss or other disposition of the investigational product, including batch or code numbers, and account for it's disposition on a subject-by-subject basis, including specific dates and quantities. The source document, documenting the subject's participation in this randomized clinical trial, must be documented in the medical and research records. Destruction will be documented in accordance with institutional practices.

5.6 Packaging and Labels: Bottles are labeled to comply with study requirements and applicable regulations for investigational drug use. Bottle labels include agent name, protocol number, dosing and storage instructions, required warnings for restricted, investigational use, and spaces for recording the subject registration and randomization number. The study agent to be used, Lovaza® (omega-3-acid ethyl esters), an FDA-approved prescription omega-3 provides prescription-only potency and purity with each 1-gram Lovaza® (omega-3-acid ethyl esters) gel capsule contains 90% omega-3-acid ethyl esters; 84% eicosapentaenoic acid (EPA) and docosahexaenoic acid (DHA) ethyl esters. Lovaza® is provided by GlaxoSmithKline, who has authorized the FDA center for Drug Evaluation and Research, Division of Metabolic and Endocrine Drug Products to reference Lovaza® Capsules IND # 45,998. An investigator-initiated IND will be cross filed by the PI for this clinic trial

5.7 Drug Storage of COGNUTRIN (VITABLUE and n-3 fatty acids): All investigational agents will be received, stored and dispensed by the Investigational pharmacy at MCC. Bottles with study agent will be stored at controlled room temperature (15-30 0 C).The PI, or a responsible party designated by the investigator, will maintain a careful record of receipt, disposition, and return of all study agent on the Investigational Agent Accountability Record. All study drug supplies will be kept in a locked limited access room. The study drug must not be used outside the context of the protocol. Under no circumstances will the investigator or .other site personnel supply study drug to other investigators, patients, or clinics, or allow supplies to be used other than directed by this protocol. Study agent may not be transferred from one patient to another, from one participating center to another participating center or from one protocol to another. All other transfers (i.e. patient or PI moves) must be approved in advance by the study PI. Every attempt will be made to collect all unused study agent supplies to be returned to the Moffitt Research Center PI office. The investigator will maintain records documenting the receipt, use, loss or other disposition of the investigational product, including batch or code numbers, and account for it's disposition on subject-by-subject basis, including specific dates and quantities. The source document, documenting the subject's participation in this clinical trial must be documented in the medical and research records. Destruction will be adequately documented.

5.8 Registration and Randomization: Potential subjects will be screened by the research coordinator using an Eligibility Checklist (Appendix I). The initial screening visit will verify patient eligibility to the study. A minimum of 40 subjects will be randomized to the pilot clinical trial. Within 6 months of completion of treatment with chemotherapy and radiation if applicable, we will screen the patients for cognitive function to determine the eligibility of participants to participate in the randomized trial portion of the study. If found eligible based on the criteria established for cognitive impairment, subjects will be ready for baseline data collection.

The research staff will use the Demographic Questionnaire Form to obtain baseline demographic data, medical and family history, and information regarding other health habits such as alcohol, tobacco and previous nutritional supplement use. Clinical Research Form (CRF): All medical record data (CRF) pertaining to the cancer diagnosis, tumor characteristics, node involvement, stage confirmation, medical history of cancer, menstrual cycle information, other medical history including renal or liver disease, concomitant medications including treatments for cancer and autoimmune diseases will be obtained from all subjects at baseline and changes in these variables monitored. Once clinical eligibility is confirmed, and informed consent is signed, randomization of subjects takes place within the Moffitt SRARS program. SRARS is a web delivered application that records subject registrations and provides randomization assignments. Subjects will be randomized to one of 2 groups. An email is sent to a list of pre-determined recipients (clinical research coordinators) stating the treatment/randomization assigned to the subject.

5.9 Blinding and Unblinding Methods: All requests to unblind treatment assignment will be directed to the Protocol Lead Investigators ([name], Moffitt Cancer Center & Research Institute, [contact], [contact], e-mail: [contact] . [name] will determine if disclosure of treatment assignment is required after consultation with the Medical Doctor who is the primary MD for the subject. If disclosure of the treatment would affect important medical decisions in a subject experiencing an AE, or could affect decisions regarding safe conduct of the clinical trial, unblinding might be allowed. If disclosure is warranted, the site will be directed to the product label found in the subject's CRF binder or other designated research record. The label has a scratch-off area that will disclose the treatment assignment. Each site will document the unblinding process in the patient chart.

6. AGENT ADMINISTRATION:

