5.1 COGNUTRIN: The choice of the supplement to use in this trial is based on relevant research supporting the various components as well as the use of a commercially available dietary supplement. The supplement to be used will be a combination of 2 standardized formulations (a) antioxidants from blueberry extracts - VitaBlue™ (40% polyphenolics, 12.5% anthocyanins from blueberries (BB) and (b) omega 3-fatty acids - Lovaza®. The standardized agent - Lovaza is manufactured by Glaxo Smith Kline and will be purchased for use in this study. However, the blue berry anthocyanins was purchased from a standard manufacturer and encapsulated at the dose for this specific study using FDA standards in a certified formulary and tested by an independent laboratory for composition (FDA IND 116424). The matching placebos were also manufactured for this study using FDA standards- all of which have been evaluated and approved for use by the FDA. As indicated in the protocol, these are 2 separate products administered separately (pages 8-11). The combination that will be used has met the standards of the FDA and an IND has been approved by the FDA (FDA IND 116424) for use of this agent combination in this study. Our team took into consideration the high patient burden to the subjects due to large size if the agents were combined into one capsule and thus decided to keep them as 2 separate agents.

The supplement COGNUTRIN is a term coined by the PI to denote the combination of 2 standardized formulations (a) VitaBlue™ (40% polyphenolics, 12.5% anthocyanins from blueberries (BB) and (b) n-3 fatty acids- Lovaza®. We have obtained IND (FDA IND 116424) from the FDA for this current indication proposed from the FDA. We have not submitted a patent for this product but hope to explore the potential to license this combination if successful in the future. We are currently working on obtaining a registered trademark with this name that we coined –COGNUTRIN. Our goal is to develop this combination agent scientifically, maintain exclusivity and to not be confused with myriads of supplements in the market place.

5.1.1 VitaBlue™ (BB Anthocyanins): VitaBlue™ is a freeze dried high potency extract from blueberries. VitaBlue™ is created using a unique proprietary process from VDF FutureCeuticals. It comes as a standardized powder containing blueberry anthocyanins that is ready for encapsulation.

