6.1 Dose Regimen and Dose Groups: Intervention groups

6.1.1 Placebo Group: All participants in the placebo arm will receive the multivitamin supplement and the cognitive battery tests and structural and resting-state functional imaging at baseline and 3 months. The placebo group used herein will allow us to generate information regarding the reliable change index, so information regarding the naturalistic change in cognitive performance, as well as the potential for practice effects to influence mean-level change data, across the follow-up period is important.

6.1.2 Nutritional Supplement Group (NS): The choice of the supplement to use in this trial is based on relevant research supporting the various components as well as the use of a commercially available standardized dietary supplement of anthocyanins and n-3 fatty acids. The supplement to be used is a standardized formulation of blueberry extract VitaBlue® (40% polyphenolics, 12.5% anthocyanins from blueberries. The supplement will in addition include Lovaza® (omega-3-acid ethyl esters), an FDA-approved prescription omega-3 provides prescription-only potency and purity with each 1-gram Lovaza® (omega-3-acid ethyl esters) gel capsule contains 90% omega-3-acid ethyl esters; 84% eicosapentaenoic acid (EPA) and docosahexaenoic acid (DHA) ethyl esters. Lovaza® is provided by GlaxoSmithKline, who has authorized the FDA center for Drug Evaluation and Research, Division of Metabolic and Endocrine Drug Products to reference Lovaza® Capsules IND # 45,998. An investigator-initiated IND has been obtained by PI for use of these agents in this clinical trial (IND # 116424). Subjects in the supplements treatment arm of the study will be given in the same fashion and time table to the "placebo" patients as the active treatment patients.

6.2 Agent Administration: Intervention will be administered to the patient on an outpatient basis and self-administered by the participants. The daily dose of will be taken in divided doses (Lovaza® 2 tablet BID and Vitablue™ 2 tablet TID). On the day of monthly follow-up visit, capsules should be taken within 4 hours of visit and blood draw for required lab work.

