Two bottles containing Lovaza and 1 bottle of anthocyanins capsules will be dispensed to all participants upon randomization with adequate number of capsules, to ensure that the subject has sufficient study drug to last until the next planned clinic visit. At baseline and at each monthly visit up to the 3-month final visit, participants will receive these supplements in person to take home with them. At that point, participants will receive instructions regarding how many supplement pills they are to take a day.

Schedule of dose administration of study agents

Arm of Study	Breakfast	Lunch	Dinner
Treatment arm	2 tablets Lovaza 2 tablets Vitablue	2 tablets Vitablue	2 tablets Lovaza 2 tablets Vitablue 1 tablet multivitamin/mineral
Placebo arm	4 tablets matching placebo tablets	2 tablets matching placebo	4 tablets matching placebo tablets 1 tablet multivitamin/mineral

6.3 Contraindications: COGNUTRIN ingredients - n-3 fatty acids may be contraindicated in subjects with bleeding disorders and anthocyanins may be contraindicated in people who are sensitive or allergic to berries.

During study participation, subjects will be instructed to limit their consumption of the following berries to 1 cup per day: blackberry, blueberry, chokeberry, black currant, elderberry, and black raspberry. They will be asked to limit their consumption of the following omega 3's to 2-3 servings (4 oz per serving) a week: walnuts, flaxseed oil, canola oil, fish oils, and fatty fish such as salmon, trout, mackerel, herring, sardines, pilchards, kipper, eel, whitebait, fresh tuna, anchovies, swordfish, bloater, cacha, carp, hilsa, jack fish, katla, orange roughy, and pangas.

6.4 Concomitant Medications: During study participation, subjects will be instructed to suspend consumption of additional supplements containing anthocyanins or omega 3's. Subjects are considered enrolled in the trial from the time that the informed consent document is signed until the time that the subject is off study. All medications (prescription and over-the-counter), taken by the participant while on study will be documented on the concomitant medication CRF and will include: start and stop date, dose and route of administration, and indication.

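### VitaBlue strength, daily total and schedule do not agree: 0.47 g per capsule gives 1.4 g/day at one capsule per intake, but two units three times a day are scheduled (2.82 g/day)

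*Combined protocol and SAP*

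**What the plan says.** Section 5.2.2 gives the dose rationale for the blueberry component and ends: "We will thus use a dose of 0.47 grams/capsule dose of anthocyanins TID to total 1.4 grams per day". Section 6.5, in the part on reducing risk from the study agent, repeats the sentence. In both places the figure follows a comparator study described as giving 1.4 g/day at 0.47 g per capsule three times daily.

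Section 6.2 sets the regimen as "Vitablue™ 2 tablet TID". Its schedule table lists "2 tablets Lovaza 2 tablets Vitablue" at breakfast in the active arm, with two VitaBlue units at lunch and two more at dinner. The placebo row has "4 tablets matching placebo tablets" at breakfast, two at lunch and four at dinner.

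Sections 5.1 and 6.1.2 describe VitaBlue as "40% polyphenolics, 12.5% anthocyanins from blueberries". Section 5.2.2 puts usual dietary anthocyanin intake at 100 mg/day. Section 6.5 says twice that the substances supplied are not far above what people ordinarily eat.

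**The concern.** The rationale and the schedule imply contents per VitaBlue unit that differ by a factor of two. A reader who takes the strength from Section 5.2.2 and the count from Section 6.2 arrives at a daily amount that the protocol never states.

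This is the amount of one of the two active agents. The pilot exists to inform a larger trial, and that trial could not take its dose from this text. The reassurance about dietary amounts sits in the risk section, and whether it is true depends on which quantity the grams refer to.

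**Working it through.** **Inputs**
- Strength 0.47 g per capsule, three times daily, total 1.4 g/day: Sections 5.2.2 and 6.5.
- VitaBlue two units three times daily; Lovaza two units twice daily: Section 6.2 and its table.
- Lovaza 1 g per capsule (Sections 5.1.2 and 5.6), total 4 g/day (Section 5.2.1).
- VitaBlue 12.5% anthocyanins: Sections 5.1 and 6.1.2.
- Dietary anthocyanins 100 mg/day = 0.1 g/day: Section 5.2.2.

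**Formula:** daily amount = grams per unit x units per intake x intakes per day.

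**1. The stated total.** 0.47 x 1 x 3 = 1.41 g/day. It reproduces, to rounding, with one capsule per intake.

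**2. The scheduled count.** 0.47 x 2 x 3 = 2.82 g/day, and 2.82 / 1.41 = 2.

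**3. Is the count a slip?** The placebo row has 4 + 2 + 4 = 10 units a day. The active row has 4 Lovaza + 6 VitaBlue = 10. One VitaBlue unit per intake would need 4 + 3 = 7. The text and both table rows therefore agree on six VitaBlue units.

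**4. Do counts in Section 6.2 multiply the capsule strength?** For Lovaza, 1 x 2 x 2 = 4 g/day, exactly as stated. The word tablet does not separate the products, because Section 6.2 uses it for the Lovaza gel capsules too.

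**5. What would make total and schedule agree?** 0.47 / 2 = 0.235 g per unit, and 0.235 x 6 = 1.41 g/day. No section gives a unit of that strength or says that two units make up 0.47 g.

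**6. Anthocyanins or extract?** Ratio to the dietary figure:

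| Reading of the grams | Anthocyanins per day | Ratio to 0.1 g/day |
|---|---|---|
| Anthocyanins, stated total | 1.4 g | 14 |
| Extract, 0.47 g per intake | 1.41 x 0.125 = 0.176 g | 1.8 |
| Extract, 0.47 g per unit | 2.82 x 0.125 = 0.353 g | 3.5 |

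Taken as anthocyanins, one capsule would need 0.47 / 0.125 = 3.76 g of extract, or 0.235 / 0.125 = 1.88 g on the two-unit reading. The extract weight per capsule is not given.

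**7. Does other text settle it?** Section 6.2 dispenses "Two bottles containing Lovaza and 1 bottle of anthocyanins capsules" without a capsule count. Section 5.6 says "Bottle labels include agent name, protocol number, dosing and storage instructions" but does not give the instructions. Section 5.1 says the product was "encapsulated at the dose for this specific study using FDA standards in a certified formulary and tested by an independent laboratory for composition", but no result is reported.

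**The case against.** The strongest defence has two parts. First, the trial's own sentence adds the word dose after the per-capsule figure, so it might mean 0.47 g per dosing occasion, made up of two units. Second, the protocol often uses anthocyanins as a name for the product: in Section 5.1, in the titles of 5.1.1 and 5.2.2, and in the dispensing text of 6.2. Together these give 0.47 g of product per intake and 1.41 g of product a day. The six-unit schedule then holds, and anthocyanin intake is about 1.8 times the dietary figure, which arguably fits Section 6.5. The extract weights in step 6 also sit awkwardly with the worry in Section 5.1 about capsule size.

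This part stands. A reader might infer that no reading makes all the sections true, and the documents do not support that. The reading is strained, however. The comparator sentence just before it uses the same per-capsule expression for a regimen whose total requires one capsule per intake, and the two-unit meaning is stated nowhere.

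A reader might also set these amounts against the 0.5-2.0 g/day for 7 days cited in Section 5.2.2 and conclude that 2.82 g exceeds that experience, or that the extract readings fall below it. Either conclusion assumes that the cited grams are pure anthocyanin. The documents do not show this, and the 1.4 g/day comparator is tied to a branded product. The comparison is not relied on here.

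It is also fair that the unit count is consistent throughout Section 6.2, that the capsules were made for the study and tested, and that no endpoint or analysis uses the figure.

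**Conclusion.** The strength and total in Sections 5.2.2 and 6.5 conflict with the schedule in Section 6.2 by a factor of two: 1.41 against 2.82 g/day at 0.47 g per capsule. This rests only on taking grams per capsule as worded and on the unit counts. It does not depend on whether the grams are anthocyanins or extract.

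Whether they are anthocyanins or extract is an ambiguity, not a second contradiction. The conflict with the dietary statements is conditional on it: clear at 14 times if the grams are anthocyanins, as worded, and arguable at 1.8 to 3.5 times if they are extract.

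A reader might infer that participants received 2.82 g/day, or that the comparison between arms is biased. The documents show neither. The 2.82 g is a product of two stated figures and not a record of what was dispensed, and the unit counts are the same in both arms.

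**What to change.** The sponsor should reconcile Sections 5.2.2, 6.2 (text and table) and 6.5 against the verified capsule composition. The protocol should then state, in one place:
- extract weight and anthocyanin content per unit;
- units per intake and intakes per day;
- the daily total, and whether it is extract or anthocyanins.

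Other sections should use those figures, and both dietary statements in Section 6.5 should be made to agree with them. Which figure is right is for the sponsor to establish from its records; none is proposed here.

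The cost is a wording amendment and a check against the composition tests that Sections 5.1 and 5.3 say were done. Design, sample size and analysis are unaffected.

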7.4 Evaluations during Study Intervention

- 7.4.1 **Weeks 3, 7, 11:** Participants will be contacted reminding them to complete diet survey and to bring completed survey, study agent /symptom logs and all left over study agent (including multivitamin) to their next in person visit scheduled.
- 7.4.2 **Weeks 4 & 8 (+/- 7 days):** Participants will come in person monthly for the following:
 - 7.4.2.1 Review of completed diet surveys, study agent/symptom logs, adverse events and concomitant medications by CRC and verified with CRU RN.
 - 7.4.2.2 Collection of any unused nutritional supplement/ placebo and multivitamin for pill counts
 - 7.4.2.3 Safety labs (CBC, CMP, PT/PTT, and LDL) will be drawn
 - 7.4.2.4 Participant will be supplied with a new one-month supply of nutritional supplement or placebo

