7.5 Evaluations at Completion of Study Intervention (3 months, +/- 7 days)

- 7.5.1 Blood will be drawn for CBC, CMP, PT/PTT, and LDL and measurement of plasma antioxidant biomarkers or oxidative stress and inflammation.
- 7.5.2 A limited physical exam will be conducted, including anthropometric measurements, ECOG, concomitant medications and adverse event collection by CRC and verified with CRU RN.
- 7.5.3 Food records and study agent and symptoms logs will be collected and reviewed with subject for clarification.
- 7.5.4 The following questionnaires will be completed: Godin-Leisure Time Exercise, Patient's Assessment of Own Functioning Inventory (PAOFI); Personal Health Questionnaire (PHQ-9), and Symptoms of Fatigue and Depression (FSI) will be completed.
- 7.5.5 Cognitive testing will be administered (HVLТ-R: Form 2, COWA: T2, Color Trails Part 1& 2, Digit Span, SDMT, BVMT-R: Form 2, and Rey Complex Figure Copy).
- 7.5.6 Left over study agent will be collected and pill counts done.
- 7.5.7 Subjects will also undergo a structural and resting-state functional magnetic resonance Imaging (MRI/fMRI).

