For each subject, AE's will be collected at the screening, Month 1, Month 2, Month 3/EOT, visits as well as at the 7-day post-treatment follow-up call by the clinical research coordinator. AE's collected at the screening visit will be catalogued as baseline symptoms by the clinical research coordinator and the AE log will be reviewed and signed by either the patient's medical oncologist or PI. AE's collected during Month 1 and 2 visits will be reviewed with the patient by the nurse who drew their blood at CRU and the AE log will be signed by the principal investigator. Finally, at the Month 3 visit, the participant's medical oncologist will review the AE log with the patient and sign-off on the reported symptoms; if the medical oncologist is unavailable to sign the AE log at this visit, then the PI will review and sign the form. AE's reported at the 7-day follow-up call will be reviewed and signed by the PI. The participant's reported symptoms at this time point will be documented on a powerchart telephone note by the clinical research coordinator. Serious adverse events (SAE's) are reported to IRB and FDA. If a participant reports an SAE, the PI will immediately be informed and she will then report it to the IRB and FDA. AE logs will be scanned to patients' medical records by the clinical research coordinator once they are off-study.

7.7.9 Assessment of Cognitive Performance.

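### Section 5.8 emails the assignment to the role that collects adverse events; read literally this conflicts with the concealment in 5.9, and the plan does not say that the email is coded

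*Combined protocol and SAP*

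**What the plan says.** Section 5.8 (Registration and Randomization) has subjects assigned to one of two groups in a web application and then states: "An email is sent to a list of pre-determined recipients (clinical research coordinators) stating the treatment/randomization assigned to the subject". It does not say whether the message names the arm or gives a number.

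Section 5.9 (Blinding and Unblinding Methods) comes next and treats the assignment as hidden. Unblinding requests go to the lead investigators, and disclosure is decided after consultation with the subject's primary physician. Only if disclosure is judged warranted is the site sent to a label filed with the subject's research record: "The label has a scratch-off area that will disclose the treatment assignment". Section 5.1 describes matching placebos, so masking is clearly intended.

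AEs are collected by the same role that receives the email:
- Section 7.4.2.1 (weeks 4 and 8) has review of "adverse events and concomitant medications by CRC and verified with CRU RN".
- Section 7.5.2 (end of intervention) has "concomitant medications and adverse event collection by CRC and verified with CRU RN".
- Section 7.7.8 places collection at the screening, month 1, month 2 and month 3 "visits as well as at the 7-day post-treatment follow-up call by the clinical research coordinator".

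Others also contribute. Under 7.7.8, events "collected during Month 1 and 2 visits will be reviewed with the patient by the nurse who drew their blood at CRU". At month 3 the participant's "medical oncologist will review the AE log with the patient and sign-off on the reported symptoms", with the principal investigator (PI) standing in if the oncologist is unavailable. Events from the 7-day call are reviewed and signed by the PI. Participants keep a daily symptom log (7.7.6), safety laboratory work is done by the clinical laboratories (7.7.11), and site investigators judge severity and seriousness (10.1.4).

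**The concern.** If coordinators are told the arm at randomization, the controlled release in 5.9 does nothing for them. They would ask about symptoms, go through the logs and record events knowing who is on active agent. Several of the events that section 6.5 lists as examples, such as nausea, gas and abdominal pain, depend partly on how the question is put and what is judged worth recording.

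Incidence and severity of AEs is the primary safety endpoint (8.1, 12.6). Section 6.5 speaks of a formal safety comparison between arms. Section 12.6 plans only summaries by category and grade, and proportions with exact 95% confidence intervals, with no test between arms. Even a descriptive contrast of active against placebo is easier to trust when the person eliciting symptoms does not know the arm.

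**Working it through.** There is no figure in the plan to reproduce. The check is a reading of the sections against each other, followed by a count.

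**1. What the email contains.** Section 5.8 speaks of allocation to one of two groups and then of an email giving the treatment or randomization assigned. In that sequence the literal reading is the group. A coded reading is possible: section 5.6 gives bottle labels "spaces for recording the subject registration and randomization number", and section 5.7 requires records of batch or code numbers. Neither section links those numbers to the email.

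**2. Against 5.9.** If the email names the arm, 5.8 releases routinely to coordinators what 5.9 releases only by exception. The two cannot both operate as written. If the email carries a code, they are compatible.

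**3. Recipients and collectors.** The named recipients in 5.8 are clinical research coordinators, and the named collector in 7.4.2.1, 7.5.2 and 7.7.8 is the clinical research coordinator. The match is of role. The documents do not show that the same individuals do both.

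**4. How many collections could be affected.** The screening collection precedes randomization and drops out.

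| Collection after start of agent | Inside the 12.6 window (ends with the intervention) | Other person named |
|---|---|---|
| Month 1 | yes | Research-unit nurse verifies (7.4.2.1) and reviews with the patient; PI signs (7.7.8) |
| Month 2 | yes | As month 1 |
| Month 3 | yes | Research-unit nurse verifies (7.5.2); oncologist reviews with the patient, or the PI reviews (7.7.8) |
| 7-day call | no | PI review and signature only (7.7.8) |

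- Coordinator collections after start of agent: 3 monthly + 1 call = 4.
- Inside the 12.6 window: 4 − 1 = 3.
- Of those 3, with nurse verification: 2 (7.4.2.1) + 1 (7.5.2) = 3.
- Without nurse verification: 4 − 3 = 1, the 7-day call, which lies outside the window.

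**5. Result under each reading.**
- Email names the arm and goes to the coordinators who collect AEs: 4 of 4 collections are made by someone who knows the arm, 3 of them counting towards the primary safety endpoint.
- Email is coded: 0 of 4 are unmasked by this route.

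The documents give no basis for converting either count into a bias in AE rates.

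**The case against.** The best case against the point is that 5.9 makes sense only if site staff do not already hold the arm. Read with the matching placebos in 5.1, the randomization number in 5.6 and the code numbers in 5.7, the phrase in 5.8 may be loose wording for a coded assignment. The recipients might also be coordinators who never collect AEs. Every collection that counts towards the endpoint has nurse verification, participants' own daily logs and laboratory results do not pass first through a coordinator's questions, and 12.6 plans no test between arms in a pilot of 20 per arm.

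Much of this stands, and it limits the point. It does not remove it. No supplied passage says that the email is coded or separates recipients from collectors, and someone configuring the system from 5.8 alone could reasonably send the arm. The logs are reviewed by the coordinator (7.4.2.1), and a second reviewer works partly from what has already been recorded.

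A reader might go further and infer that the blind is broken. The documents do not support that, because the coded reading remains open. A reader might also infer, from the lack of any list of masked roles, that the nurse, oncologist, PI and site investigators are unmasked. That does not follow: 5.8 does not name them as recipients, and silence on their masking is missing detail, not a consequence of the email. Title pages and appendices were not available for this review, so a masking statement there cannot be ruled out.

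**Conclusion.** The point holds in conditional form and should be fixed. As written, 5.8 discloses the assignment to the role that collects AEs, and 5.9 conceals it. On the literal reading all 4 post-start collections are affected, 3 of them within the 12.6 window; on the coded reading none is. This rests on two assumptions that the documents leave open: that the email names the arm, and that its recipients are the coordinators who collect AEs. Confidence is medium for that reason.

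The size and direction of any bias in AE incidence or severity cannot be derived. Nor should the point be stretched to the cognitive endpoint. Section 7.7.9 has the tests given and scored by trained research personnel, and the documents do not say whether these are the coordinators who receive the email.

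**What to change.** - **Section 5.8:** send the arm assignment only to the Investigational Pharmacy, which already dispenses all agents (5.7). Send coordinators confirmation that the subject has been randomized, with a number that does not reveal the arm.
- **Section 5.9:** state that staff who collect or verify AEs are masked, so that the two sections agree.
- **If the email is already coded:** one sentence in 5.8 saying so is enough.

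The cost is small: no added visits, subjects or data. The documents do not say how the pharmacy now learns the assignment, so it must be added to the recipient list if it is not on it, and the email content may need to be reconfigured. Whether the system allows that easily is not stated.
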